But to date there are no studies regarding the lowest effective optimal dosing as an adjuvant which can aid in analgesia and also facilitate earlier discharge from hospital avoiding nerve catheter. If an effective optimal dosing of dexamethasone as an adjuvant is deciphered, it will help in avoiding costs associated with liposomal bupivacaine facilitating earlier discharge and extending post operative analgesia avoiding narcotics.

3) Setting of the Human Research

Prospective triple blinded randomized control trial in patients undergoing elective arthroscopic shoulder surgeries. The research study will take place at Mount Sinai West hospital. The site PI is [name] MD.

 Mount Sinai	Protocol Title:	COMPARISON OF THE ANALGESIC EFFICACY OF A SINGLE SHOT INTERSCALENE BLOCK WITH LIPOSOMAL BUPIVACAINE TO BUPIVACAINE WITH DEXAMETHASONE AS AN ADJUVANT-A RANDOMIZED CONTROLLED TRIAL
	Principal Investigator Name/Contact Info:	[name] MD. [name] [name]. [name] MD, PHD [name] MD [contact]
	Primary Contact Name/Contact Info	[name] MD. [contact]
	Date Revised:	
	Study Number:	

4) Resources Available to Conduct the Human Research

For n=100, the feasibility of recruitment is manageable. Recruitment will be done through a coordination of the operating schedule and the surgeon's office.

The staff members on this protocol are all employees of Mount Sinai and will either be a resident or attending physicians that are included on the IRB protocol. There are four primary members of the research personnel:

a) [name] – Roles for [name] in this study include serving as primary investigator responsible for study design and planning, data collection, subject recruitment, manuscript writing and preparation, data analysis, safety monitoring, and responding to adverse events and/or complications. She is certified in PPHS/IRB protocols, all Citi/IRB required training in human subject protection, and has prior clinical research experience. She is also a board certified anesthesiologist and professor and chair of anesthesiology with the Icahn School of Medicine and the Mount Sinai Health System.

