	Principal Investigator Name/Contact Info:	[name] MD. [name] [name]. [name] MD, PHD [name] MD [contact]
	Primary Contact Name/Contact Info	[name] MD. [contact]
	Date Revised:	
	Study Number:	

patients will be randomized using computer generated tables and sealed envelopes. A designated resident not involved in the study will open the sealed envelope and randomize the patient into the following groups:

Group A—Liposomal bupivacaine(133mg bupivacaine diluted normal saline total 25cc)

Group B---Dexamethasone 4mg in 0.5% Bupivacaine 25cc

The patients will be transferred to the OR to proceed with the surgery. Standard ASA monitors will be placed again and after pre oxygenation, general anesthesia will be induced with propofol and fentanyl. Laryngeal mask airway of appropriate size will be inserted and patient will be connected to the ventilator for the procedure. Maintenance of anesthesia will be achieved with sevoflurane and oxygen/air mixture. Once the procedure is completed, patients will be extubated and transferred to the recovery room(PACU) for post anesthetic care.

The patient will also receive 4mg of ondansetron intra-venous in the OR as prophylaxis for post operative nausea and vomiting.

Patients, attending anesthesiologists, surgeon and research assistant collecting the data will be blinded of the group assignment. The medication solution will be prepared by the resident physician.

 Mount Sinai	Protocol Title:	COMPARISON OF THE ANALGESIC EFFICACY OF A SINGLE SHOT INTERSCALENE BLOCK WITH LIPOSOMAL BUPIVACAINE TO BUPIVACAINE WITH DEXAMETHASONE AS AN ADJUVANT-A RANDOMIZED CONTROLLED TRIAL
	Principal Investigator Name/Contact Info:	[name] MD. [name] [name]. [name] MD, PHD [name] MD [contact]
	Primary Contact Name/Contact Info	[name] MD. [contact]
	Date Revised:	
	Study Number:	

Pain scores in the form of NRS (NUMERICAL RATING SCALE) will be assessed on arrival to PACU. Pain scores will also be assessed 1 hour after arrival to PACU and at the time of discharge from PACU. NRS scores will be assessed on the floors every 6 hourly during the first 24 hours, 8 hourly and then every 12 hourly during the second 24 hours. If NRS scores are more than 5 at any time a one-time dose of oxycodone 10mg and Tylenol 1000 mg will be given.

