Once the primary team discharges the patient, a telephone follow - up every day until resolution of any residual arm weakness/numbness will be done by the anesthesia resident originally involved in the surgery.

Patients will also be asked to note the time to first analgesic request in addition to onset of sensory discomfort and motor recovery.

a) Recruitment Methods

See above. With the HIPAA waiver requested, the surgeon will provide investigators (both of whom are physicians within the department of Anesthesiology) with information of eligible patients. After the operating room schedule has been reviewed for potential participants in the study the contact information will be obtained through the surgeon's office. Subjects will be called by the department of Anesthesiology when their surgery is scheduled, and they will be informed about the study then.

 Mount Sinai	Protocol Title:	COMPARISON OF THE ANALGESIC EFFICACY OF A SINGLE SHOT INTERSCALENE BLOCK WITH LIPOSOMAL BUPIVACAINE TO BUPIVACAINE WITH DEXAMETHASONE AS AN ADJUVANT-A RANDOMIZED CONTROLLED TRIAL
	Principal Investigator Name/Contact Info:	[name] MD. [name] [name]. [name] MD, PHD [name] MD [contact]
	Primary Contact Name/Contact Info	[name] MD. [contact]
	Date Revised:	
	Study Number:	

b) Inclusion and Exclusion Criteria

Inclusion criteria: All patients between age 18-75 years undergoing primary shoulder arthroscopic procedure. All patients who speak read and understand English will be included for follow up purposes.

Exclusion criteria included patients with patient refusal, ASA 5, presence of coagulopathy, severe lung disease, contralateral diaphragmatic palsy, insulin-dependent diabetes, hepatic disease/failure, kidney disease/failure, pregnancy, chronic opioid use (defined as opioid use for >3 months), or allergy to any of the study medications.

c) Number of Subjects

N= 100, recruit ability is manageable. Based on previous study conducted by Tandoc et al with estimated average duration of analgesia at 22 hours with dexamethasone in 0.5% bupivacaine and assumed average SD of 3 hours, they estimated that 16 patients would be needed to provide 80% power to conclude absence of effect at the significance level of 0.05 among treatment groups. To allow for 20% patient dropouts, 30 subjects per group will be targeted for enrollment.

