Data collected in excel file to be de-identified after initial collection. Excel file be subsequently encrypted and shared only between the two above listed investigators via secure Mt. Sinai (chpnet) electronic mail.

The information included in the data will be medical record number, age, gender, ASA class, type of surgery, pain score assessments, duration of surgery, anesthesia time, time to first narcotic, total narcotic use and pain scores up to 48 hours after surgery. In case of known history of type 1 or 2 diabetes, preoperative and post operative finger stick will be recorded. Time of administration of study drug, smoking status and patient satisfaction scores will also be recorded. Only the research personnel will have access to the data. The data will be stored as a hard copy files and on a secure spreadsheet. The research personnel are responsible for the receipt of the data. The PI will keep the hard copies secure and any electronic data will be encrypted. No personal identifiers will be used. The data will undergo statistical analysis.

i) Provisions to Monitor the Data to Ensure the Safety of subjects

 Mount Sinai	Protocol Title:	COMPARISON OF THE ANALGESIC EFFICACY OF A SINGLE SHOT INTERSCALENE BLOCK WITH LIPOSOMAL BUPIVACAINE TO BUPIVACAINE WITH DEXAMETHASONE AS AN ADJUVANT-A RANDOMIZED CONTROLLED TRIAL
	Principal Investigator Name/Contact Info:	[name] MD. [name] [name]. [name] MD, PHD [name] MD [contact]
	Primary Contact Name/Contact Info	[name] MD. [contact]
	Date Revised:	
	Study Number:	

Part I: Elements of Data and Safety Monitoring Plan

MSSM Principal Monitor:

Last Name: [name]

First Name: [name]

Academic Title: Attending Physician, Professor

Department: Anesthesiology

Mailing Address: Mount Sinai West [name]

[contact]

Fax:

E-mail: [contact]

MSSM Principal Monitor:

Last Name: [name]

First Name: [name]

Academic Title: Attending Physician, Assistant Professor

Department: Anesthesiology

Mailing Address: Mount Sinai West [name]

[contact]

Fax:

E-mail: [contact]

Last Name: [name]

First Name: [name]

Academic Title: Attending Physician, Professor

Department: Orthopedics

Mailing Address: Mount Sinai West [name]

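### Does the silence on whether the resident making post-discharge calls is blinded undermine the triple-blind design?

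*Combined protocol and SAP*

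**What the plan says.** Sections 3 and 5 of the combined protocol and SAP describe the trial as triple blinded. The relevant statements on roles are these.

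- **Allocation (Section 5):** "A designated resident not involved in the study will open the sealed envelope and randomize the patient into the following groups".
- **Preparation (Section 5):** "The medication solution will be prepared by the resident physician". Which resident is not stated.
- **Blinded roles (Section 5):** "Patients, attending anesthesiologists, surgeon and research assistant collecting the data will be blinded of the group assignment".
- **After discharge (Section 5, just before a) Recruitment Methods):** daily telephone follow-up until any remaining weakness or numbness has gone "will be done by the anesthesia resident originally involved in the surgery". The next sentence asks patients to note their own times of first analgesic request, sensory discomfort and motor recovery.
- **Staffing (Section 4):** study staff "will either be a resident or attending physicians that are included on the IRB protocol".

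Section 1 lists time of motor recovery under Primary Outcome, and arm weakness and numbness (0 to 24 and 24 to 48 hours) under Secondary Outcome. Section 5 c) puts duration of motor block into the Kaplan-Meier and Cox analyses. Section 5 e) names a different primary end point, first analgesic request in the first 24 hours.

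**The concern.** Residents open the envelope, prepare the solution, perform the block and make the calls. Only the first of these is expressly kept apart from the study. No available sentence says that the caller is blinded or must be someone other than the preparer.

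The calls follow the same condition that defines motor recovery, and under Section 5 d) participation lasts until weakness has resolved. A recovery that comes after discharge could therefore be dated through a call. Judging by telephone whether wrist and elbow function is fully back leaves room for how the question is put and when recovery is declared complete. If the caller knew the arm, the recorded times could differ between groups for reasons unrelated to the drug, and they would enter a time-to-event analysis of an outcome listed as primary.

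The data list in Section 5 h) does not settle the source, since it names neither motor recovery nor weakness nor numbness.

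**Working it through.** The plan gives no figure on this point to reproduce. The check is a reading of the roles against the outcomes, plus one count.

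**Step 1: what bias would require.** Four conditions must all hold: (a) the caller knows the allocation; (b) the call, and not the patient's note, supplies the analysed value; (c) the event falls after discharge; (d) knowledge of the arm shifts the recorded time. If (a) or (b) fails, the route is closed.

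**Step 2: is (a) stated?** No. The only resident said to learn the allocation is the envelope opener, described as outside the study. The caller took part in the surgery. The preparer is simply the resident physician. Within the passage on allocation and blinding, the envelope opener is the only resident introduced before the preparer, so the easier reading is that they are the same person. It is not the only reading, because residents also perform the blocks.

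**Step 3: is (b) stated?** No. Data collection is attributed to a research assistant, who is blinded. Motor recovery is something the patient is asked to note, and patients are blinded. The calls are described only as follow-up until symptoms resolve, which fits ordinary clinical care after a nerve block.

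**Step 4: which outcomes could be reached under (c)?**

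| Outcome | Where listed | Exposure to post-discharge calls |
|---|---|---|
| Time of motor recovery | Section 1, primary | Only if recovery follows discharge |
| Arm weakness, numbness | Section 1, secondary, to 48 hours | Only if discharge is before 48 hours |
| First analgesic request, first 24 hours | Section 5 e), primary end point | Little; the calls concern weakness and numbness, and patients note this time themselves |

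Inpatient observation is planned well into this period: pain scores are "assessed on the floors every 6 hourly during the first 24 hours, 8 hourly and then every 12 hourly during the second 24 hours". The documents give no discharge times, so the share of patients meeting (c) is unknown.

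**Step 5: does the data list show that the call is the source?** Section 5 h) contains:

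- 11 items in its main sentence, from medical record number through "time to first narcotic, total narcotic use and pain scores up to 48 hours after surgery";
- 1 item for finger sticks in known diabetes;
- 3 items in the last sentence: "Time of administration of study drug, smoking status and patient satisfaction scores will also be recorded".

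That makes 11 + 1 + 3 = 15 items, and 0 of the 15 are motor recovery, weakness or numbness. The same list also leaves out PROMIS, sleep quality, nausea, Horner's syndrome, hoarseness, dyspnea and length of stay, all of which are Section 1 outcomes. An omission shared by so many outcomes reflects an incomplete list and says nothing particular about who records motor recovery.

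**Step 6: size.** With no discharge times, no variability for motor recovery and no evidence for (a) or (b), neither a direction nor a magnitude can be calculated.

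**The case for a change.** The strongest case for acting is that a triple-blind label promises blinded assessment and the text does not deliver it for one role. The reading that the preparer is the envelope opener is an inference, and even if it is right, no sentence says the caller is blinded. The research assistant's blinding does not clearly cover calls assigned to a resident; staff may be residents, so the two could be the same person, but nothing says they are. The patient's note is never named as the analysis source. A clarification would be cheap.

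The silence is real and this part stands. The step from silence to bias does not. The documents name a blinded source and a blinded collector, whereas the harmful reading needs two facts found nowhere in the text. The usual remedy, taking motor recovery from the patient's record through the blinded assistant, mostly restates the arrangement already implied. Ease of rewording does not turn a missing detail into a design fault.

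The personnel descriptions in Section 4 are also not fully available. Four members are announced but only the first is visible, and the rest may say who collects which data. A finding that depends on absence should carry less weight for that reason.

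**Conclusion.** No change to the plan is called for. The text leaves open which resident prepares the solution, whether the caller is blinded, and whether the calls supply outcome data. It does not show an unblinded caller or a call that dates motor recovery. The sensible way to fill the gap is the one the text points to: the patient's own note as source, the blinded assistant as collector, and the envelope opener kept out of follow-up.

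No bias is quantified. At most, the exposure concerns motor recovery in patients discharged before it is complete, and weakness or numbness in those discharged before 48 hours, both in unknown proportion. The end point in Section 5 e) is little affected.

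This conclusion rests on two assumptions: that the study follows its stated roles, with patients recording their own times and the blinded assistant collecting the data; and that the unavailable personnel text does not assign outcome collection to someone who knows the allocation. If the calls were in fact the source of motor-recovery times and were made by the preparer, the concern would be substantive.

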Data will be expressed as mean \pm SD or median with interquartile range as appropriate. Categorical data will be analyzed with Fisher exact test and chi-square test. The duration of analgesia and motor block will be analyzed by the Kaplan-Meier survival analysis and Cox

 Mount Sinai	Protocol Title:	COMPARISON OF THE ANALGESIC EFFICACY OF A SINGLE SHOT INTERSCALENE BLOCK WITH LIPOSOMAL BUPIVACAINE TO BUPIVACAINE WITH DEXAMETHASONE AS AN ADJUVANT-A RANDOMIZED CONTROLLED TRIAL
	Principal Investigator Name/Contact Info:	[name] MD. [name] [name]. [name] MD, PHD [name] MD [contact]
	Primary Contact Name/Contact Info	[name] MD. [contact]
	Date Revised:	
	Study Number:	

proportional hazards modeling. Subgroup pairwise analyses will be conducted via Kruskal-Wallis rank test with Bonferroni correction for significance. All analysis will be conducted with intent-to-treat approach to minimize the potential effects of dropout. Statistical significance will be defined as $P<0.05$.

d) Study Timelines

2018-2019 and subsequent data analysis. The subject's participation will be from time of enrollment to complete resolution of arm weakness and motor strength. Estimated date of enrollment completion will be when 100 eligible subjects are enrolled in final data analysis. Estimate date for study completion will be June 2019.

e) Study Endpoints

Primary end point will be the time of first analgesic request for the first 24 hours post operatively.

Secondary end points will be NRS at 6 hours, 12 hours, 18 hours, 24 hours, 36 hours and 48 hours and oxycodone use.

f) Procedures Involved in the Human Research

Prospective randomized controlled trial and data analysis only.
Ultrasound guided interscalene block with nerve catheter placement.

 Mount Sinai	Protocol Title:	COMPARISON OF THE ANALGESIC EFFICACY OF A SINGLE SHOT INTERSCALENE BLOCK WITH LIPOSOMAL BUPIVACAINE TO BUPIVACAINE WITH DEXAMETHASONE AS AN ADJUVANT-A RANDOMIZED CONTROLLED TRIAL
	Principal Investigator Name/Contact Info:	[name] MD. [name] [name]. [name] MD, PHD [name] MD [contact]
	Primary Contact Name/Contact Info	[name] MD. [contact]
	Date Revised:	
	Study Number:	

g) Specimen Banking

N/A

h) Data Management and Confidentiality

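### In section 5c, 30 per group does not follow from 16 patients and 20% dropout and contradicts N = 100, and the only power statement gives no difference for this trial's superiority question

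*Combined protocol and SAP*

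**What the plan says.** Section 5c (Number of Subjects) gives three figures in a row.

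- It opens with a total: "N= 100, recruit ability is manageable".
- It cites an earlier study with a mean analgesia duration of 22 hours for dexamethasone in 0.5% bupivacaine and an assumed SD of 3 hours, and reports that "they estimated that 16 patients would be needed to provide 80% power to conclude absence of effect at the significance level of 0.05". It does not say whether 16 is per group or in total.
- It ends with a target: "To allow for 20% patient dropouts, 30 subjects per group will be targeted for enrollment".

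The total of 100 appears in two other places. Section 4 says "For n=100, the feasibility of recruitment is manageable", and section 5d (Study Timelines) says "Estimated date of enrollment completion will be when 100 eligible subjects are enrolled in final data analysis".

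Section 5 (Study Design) lists two groups, A and B. On allocation it says only that "patients will be randomized using computer generated tables and sealed envelopes", without a ratio. Section 1 asks whether liposomal bupivacaine is superior. The analysis text in section 5c says "The duration of analgesia and motor block will be analyzed by the Kaplan-Meier survival analysis and Cox" proportional hazards modelling, with significance at P<0.05, and adds: "All analysis will be conducted with intent-to-treat approach to minimize the potential effects of dropout".

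**The concern.** A sample-size section should lead from a target difference to a number analysed, and from there, through dropout, to a number enrolled. Here that chain breaks at each link. No target difference is stated. The step from 16 to 30 is credited to 20% dropout alone, which does not produce 30. The 30 per group then disagrees with the total given in the same section.

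The one power statement belongs to another study. Its stated aim, concluding that there is no effect, differs from the superiority question in section 1. Its inputs are a mean and an SD, whereas the duration endpoints here are to be analysed by Kaplan-Meier and Cox methods, for which no hazard ratio or event count is given.

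What is at stake is justification and interpretation. A reader cannot tell what size of effect the trial was planned to find, and so cannot judge what a non-significant result would mean.

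**Working it through.** **Inputs.** From section 5c: 16 patients, 80% power, significance level 0.05 (sidedness not stated), SD 3 h, 20% dropout, 30 per group, N = 100. From section 5: two groups. Not given anywhere in the text available: the expected duration with liposomal bupivacaine, a difference or margin, a hazard ratio, or the allocation ratio.

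**Step 1: from 16 to 30.** The standard inflation is n/(1 − dropout).

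- 16 per group: 16/0.8 = 20. The cruder 16 × 1.2 = 19.2 also rounds up to 20.
- 16 in total: 8 per group, and 8/0.8 = 10.
- What 30 would need: 30 × 0.8 = 24 as the starting number, or a dropout of 1 − 16/30 = 46.7%.

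The plan's 30 per group is not reproduced under either reading of 16.

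**Step 2: from 30 per group to 100.** 2 × 30 = 60, which is 40 short of 100. Three groups would give 90 and four would give 120, so a forgotten arm does not explain it. Taking 100 as two equal groups gives 50 per group.

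**Step 3: can the 16 be checked?** Not forwards, because no difference is stated. Solving backwards with 16 per group and SD 3 h:

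- Two-sided superiority at 0.05 with 80% power: difference = SD × √(2/n) × (1.960 + 0.842) = 3 × √(2/16) × 2.802 = 2.97 h. The t-test version is 3.07 h.
- Equivalence by two one-sided tests, 0.05 per side, 80% power: margin = 3 × √(2/16) × (1.645 + 1.282) = 3.10 h.

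So 16 per group fits a superiority test for about 3 h (1 SD) about as well as an equivalence margin of about 3.1 h. Neither figure is in the documents. The 16 is unverifiable, not shown to be wrong.

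**Step 4: what 100 randomised can detect (guide only).** Assumptions: two-sided t-test at 0.05, 80% power, SD 3 h in both groups, 1:1 allocation.

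| Contributing per group | Basis | Normal formula | t-test |
|---|---|---|---|
| 50 | all 100 contribute | 3 × √(2/50) × 2.802 = 1.68 h | 1.70 h |
| 40 | 50 × 0.8, dropouts give no data | 3 × √(2/40) × 2.802 = 1.88 h | 1.90 h |

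The Cox figure will differ. A simulation for 40 per group (normal durations, SD 3 h, means 22 h and 22 h plus the difference, unadjusted Cox model, follow-up cut at 24 h on one reading of section 5e, 20,000 runs per point) gave 77.9% power at 2.1 h and 81.5% at 2.2 h. That puts the detectable difference near 2.2 h rather than 1.9 h. It rests on assumptions that the sponsor would have to replace.

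**The case against.** Several points on the other side have force.

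- **The 30 may be a deliberate cushion or a leftover.** An allowance for 20% dropout sets a floor of 20, and 30 exceeds it. The sentence also follows directly on the earlier study's estimate and may have been carried over from it. Either is possible, but the text gives dropout as the only reason and states the target in the future tense as this trial's own. It still needs correcting.
- **The absence-of-effect phrase may be loose drafting.** As step 3 shows, 16 per group is compatible with an ordinary superiority calculation. That stands, and it is why the 16 cannot be called wrong. The phrase still does not match section 1, and the difference is still missing.
- **The larger, more often stated number is the conservative one.** This stands, and it limits the severity.

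Some stronger readings are tempting, but the documents do not support them.

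- **That the trial is underpowered.** Fifty per group has more power than 16 or 30 per group for any given difference, and with no target difference stated no shortfall can be shown.
- **That stopping at 60 would be as much per protocol as stopping at 100.** Section 5d is the only statement of when enrolment ends, and it says 100. Sections 4 and 5c agree with it.
- **That section 5d means 100 analysed, so that more than 100 must be enrolled.** The sentence is worded as the end of enrolment. Under the intent-to-treat rule in section 5c, everyone randomised is analysed, so 100 in the analysis is 100 randomised.
- **That the trial is meant to establish equivalence.** The research question is plainly superiority, and no margin is given.
- **That 40 per group is the effective sample.** In a Kaplan-Meier or Cox analysis a dropout is normally censored and contributes time until then. Forty is a worst case and 50 is the other end of the range.

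**Conclusion.** The sample-size text is wrong as written and should be fixed. From the documents' own figures, 16 with 20% dropout gives 20 per group (or 10), not 30, and 30 in each of two groups is 60, not 100. These two failures need no assumptions. The only power statement is an earlier study's, has no difference or margin, and is not expressed for this trial's question or planned analysis. That is a gap in justification and does not show that 100 is too few.

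The detectable differences of about 1.7 h and 1.9 h are guides. They depend on the SD of 3 h applying to both groups, 1:1 allocation, a two-sided 0.05 level and a t-test in place of the planned Cox model.

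**What to change.** 1. Keep 100 as the number randomised, since three places and the only rule on the end of enrolment say so.
2. In section 5c, delete the 30-per-group target and the absence-of-effect phrase.
3. Reword section 5d to: enrolment ends when 100 patients have been randomised.
4. Replace the power sentence with one for this trial, along these lines:

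> 100 patients will be randomised in a [ratio] allocation. The Cox analysis of [the one primary endpoint] has 80% power at two-sided 0.05 to detect [difference or hazard ratio], with censoring at [follow-up limit] and dropouts treated as [rule].

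The intent-to-treat sentence can stay. The new sentence requires one primary endpoint to be settled first, because section 1 lists several primary outcomes and section 5e names time to first analgesic request over the first 24 hours. The sponsor should also say whether it considers the detectable difference clinically meaningful. Solving for a difference from a fixed N describes what the trial can do, but it does not by itself justify the N.

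**Cost.** Wording and one recalculation, with no added patients. The downside is that the stated detectable difference may be less favourable than the sponsor hoped.

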	Date Revised:	
	Study Number:	

Based on the above two options in the current opioid epidemic crisis, we propose to study the analgesic efficacy of liposomal bupivacaine to bupivacaine with dexamethasone as an adjuvant in interscalene block for shoulder surgeries. Till date, there is not study comparing the two.

1) Objectives:

Research Question:

Is the analgesic efficacy of liposomal bupivacaine superior to that of bupivacaine with dexamethasone as an adjuvant in interscalene block?

Primary Outcome: The primary outcomes is the time of analgesia duration (defined as the onset of sensory discomfort that required medication) and time of motor recovery (defined as the recovery of full motor function of both wrist and elbow on the nerve block side). Time to first analgesic request, NRS at 6 hours, 12 hours, 24 hours and 48 hours, POD 3, 4, 5, 6, 7 and total narcotic consumption.

Secondary Outcome: arm weakness (0 to 24 hours, 24 to 48 hours), arm numbness (0 to 24 hours, 24 to 48 hours), nausea, vomiting, dizziness, Horner's syndrome, hoarseness, dyspnea, Intra operative narcotic consumption, PACU and hospital length of stay, pain scores as assessed by PT on POD 1, and 2.

 Mount Sinai	Protocol Title:	COMPARISON OF THE ANALGESIC EFFICACY OF A SINGLE SHOT INTERSCALENE BLOCK WITH LIPOSOMAL BUPIVACAINE TO BUPIVACAINE WITH DEXAMETHASONE AS AN ADJUVANT-A RANDOMIZED CONTROLLED TRIAL
	Principal Investigator Name/Contact Info:	[name] MD. [name] [name]. [name] MD, PHD [name] MD [contact]
	Primary Contact Name/Contact Info	[name] MD. [contact]
	Date Revised:	
	Study Number:	

patient's satisfaction scores(Yes- I would prefer the same analgesic technique the next time or No-I would prefer a different analgesic technique) and quality of sleep (good, moderate/average, bad) on POD 0 and 1. Patient reported outcomes measurement information system (PROMIS) baseline global assessment will be conducted prior to surgery and post operative pain assessment at first follow up visit. Each patient will be assessed by standardized assessment of shoulder function as recommended by American association of shoulder and elbow surgery.

2) Background

See above. There have been several studies demonstrating efficacy of dexamethasone in prolonging the analgesic effect when administered both perineurally and intra-venously as an adjuvant to local anesthesia demonstrating a dose effect relationship.

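### Sleep quality is an ordered three-level outcome, but the only rule that covers it is Fisher/chi-square, which ignores the order and costs about 6 to 11 points of power under a uniform shift

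*Combined protocol and SAP*

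**What the plan says.** Under Secondary Outcome in section 1 (Objectives), the protocol lists "quality of sleep (good, moderate/average, bad) on POD 0 and 1". This gives three levels, ordered from best to worst, on each of two days.

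The analysis paragraph sits at the end of section 5c (Number of Subjects). On categorical outcomes it has one sentence, with no exception for ordered scales: "Categorical data will be analyzed with Fisher exact test and chi-square test". Kaplan-Meier and Cox methods are reserved for duration of analgesia and of motor block. One rank test appears, for a different purpose: "Subgroup pairwise analyses will be conducted via Kruskal-Wallis rank test with Bonferroni correction for significance". No trend test, ordinal model or rank test is assigned to sleep quality.

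**The concern.** A chi-square or Fisher test on a table of two arms by three sleep categories treats good, moderate/average and bad as three unrelated labels. Relabel or shuffle the columns and the p-value stays the same. A consistent move towards better sleep therefore gets no more credit than a change without direction, and the test comes with no estimate of how much better one arm slept.

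The research question in section 1 is directional: it asks whether one preparation is superior. Sleep on POD 0 and POD 1 covers the period in which a block with an assumed mean duration of 22 hours would wear off. The useful answer is which arm slept better and by how much, and the planned test is not aimed at that. What is at stake is some power and a usable effect estimate on one patient-reported secondary outcome.

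**Working it through.** **The plan's own figure.** There is none for sleep quality. The only power statement concerns duration of analgesia: "they estimated that 16 patients would be needed to provide 80% power to conclude absence of effect at the significance level of 0.05". The SD is 3 hours, but no difference is given, so the figure cannot be reproduced from the stated inputs alone. With an assumed difference of 3 hours, n per group = 2 × (1.96 + 0.84)² × 3² / 3² = 15.7, so 16 (power 80.7%). It matters here only because it leads to the arm sizes.

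**Inputs from the documents**
- Three ordered levels, two arms (sections 1 and 5).
- Significance level 0.05 (section 5c). Sidedness is not stated; two-sided is assumed.
- Arm size: section 5c gives both "To allow for 20% patient dropouts, 30 subjects per group will be targeted for enrollment" and "N= 100, recruit ability is manageable". The second is 50 per arm if allocation is 1:1. Since 2 × 30 = 60 is not 100, both sizes are used.

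**Inputs assumed.** Comparator distributions (good/moderate/bad, %) of 40/35/25, 50/30/20 and 34/33/33, with common odds ratios of 2.0 and 2.5. With two arm sizes this makes 12 scenarios.

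**Why order is lost.** Pearson's statistic is the sum over the six cells of (O − E)²/E, on (2 − 1)(3 − 1) = 2 degrees of freedom. Reordering the columns only reorders the terms of the sum. The Wilcoxon test compares mean ranks and puts 1 degree of freedom on a shift along the scale.

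**In theory.** For 80% power at 5%, a 1-df test needs noncentrality 7.85 and a 2-df test needs 9.63. The ratio is 7.85/9.63 = 0.81. If all the signal lies along the ordered direction, a 2-df test has 70.9% power where the 1-df test has 80%.

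**By simulation, uniform shift** (60,000 tables per scenario, tie-corrected Wilcoxon against Pearson chi-square):

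| Per arm | Chi-square | Wilcoxon |
|---|---|---|
| 30 | 21–37% | 27–47% |
| 50 | 32–58% | 41–68% |

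Within scenario the gain is about 6 to 11 points, with type I error near 5% for both tests.

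**One case in full** (100,000 tables), comparator 40/40/20 and odds ratio 2:
- Good: odds 0.40/0.60 = 0.667; × 2 = 1.333; probability 57.1%.
- Good or moderate: odds 0.80/0.20 = 4; × 2 = 8; probability 88.9%.
- The other arm is therefore about 57/32/11.
- At 30 per arm, power is 21.8% by chi-square and 28.7% by Wilcoxon (gain 6.9). At 50 per arm it is 34.4% and 44.0% (gain 9.6).
- 80% power would need 146 per arm by chi-square and 120 by Wilcoxon: 120/146 = 0.82, or 18% fewer.

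**When the shift is not uniform:**

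| Arms compared (%) | Per arm | Chi-square | Wilcoxon |
|---|---|---|---|
| 40/35/25 vs 60/15/25 (moderate to good only) | 30 | 38% | 19% |
| 40/35/25 vs 40/50/10 (bad to moderate only) | 30 | 29% | 10% |
| 40/35/25 vs 40/50/10 | 50 | 47% | 13% |
| 30/40/30 vs 45/10/45 (both extremes) | 30 | 70.2% | 5.7% |

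Here the unordered test is clearly the more sensitive.

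**The case against.** The strongest case against is that the advantage depends on the assumed pattern. Proportional odds is the setting in which a rank test does best, and the documents give no sleep distribution. In the one-directional cases in the second table one arm plainly sleeps better, yet Wilcoxon loses 19 to 34 points (38 − 19 and 29 − 10 at 30 per arm; 47 − 13 at 50), more than it gains under a uniform shift. This stands. A reader might infer that the planned test gives up power for nothing, or that changing it has no downside. The documents do not support either, because nothing in them fixes the shape of the effect.

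A reader might also infer that the trial could not say which arm slept better. That goes too far: the percentages behind the chi-square test show the direction. What is missing is a test aimed at that direction and an estimate with an interval. Wilcoxon alone would not supply the estimate either, so the fix has to ask for it separately.

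It can be said that a rank test is already in the plan, and that Kruskal-Wallis with two arms amounts to the Wilcoxon test. But section 5c ties it to subgroup pairwise comparisons, not to ordinal outcomes.

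Finally, the outcome is minor. Sleep is one item in a long secondary list, is absent from Study Endpoints (section 5e) and from the data items in section 5h, and carries no power claim. Chi-square is valid, and power stays low under either test in most of the scenarios. All of this stands and limits the weight of the point, but it does not make the unordered test the better match to a directional question.

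**Conclusion.** The point holds in a limited form. An ordered outcome is left to tests that ignore order, and no other section corrects this. Under a roughly uniform shift the cost is about 6 to 11 percentage points of power at 30 to 50 per arm, at the same type I error. That size rests on assumed distributions, a common odds ratio of 2.0 to 2.5 and a two-sided 5% level. A uniform shift is a reasonable working expectation if better analgesia improves sleep generally, but it is an expectation and not something the protocol establishes. The plan is not invalid on this point, and the primary analysis is untouched. It is a cheap improvement to a secondary outcome.

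**What to change.** In the analysis paragraph of section 5c:

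1. Limit Fisher exact and chi-square tests to binary or unordered outcomes, such as satisfaction (yes/no), nausea and Horner's syndrome.
2. State that sleep quality will be compared between arms by the Wilcoxon rank-sum test, separately on POD 0 and POD 1.
3. For each day, report each arm's percentages in the three categories, and a common odds ratio with 95% CI from a proportional-odds model for that day.

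The Wilcoxon test is in essence the score test of the proportional-odds model, so test and estimate address the same question. Fitting each day separately avoids a patient effect on only two observations per person. The number of sleep tests is still one per day, so multiplicity does not grow.

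The cost is two or three sentences, with no new data, visits or patients, provided they are written before unblinded data are seen. The price is lower sensitivity when the effect is confined to one adjacent pair of categories or goes in both directions. The reported percentages would let a reader see such a pattern.
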